5.12.2 Clinical Laboratory Parameters

Clinical laboratory test values (in SI unit) will be summarized for each assessment time point. Change from baseline values will be summarized for each assessment time point post baseline.

Clinical laboratory test values will be considered potentially clinically significant (PCS) if they meet either the lower-limit or higher-limit PCS criterion listed in [Table 5.12-2](#). The incidence of change in clinical laboratory values from non-PCS at baseline to PCS post baseline will be tabulated for patients with available non-PCS values at baseline and at least 1 assessment post baseline. A supportive listing of patients with PCS post-baseline values will be provided, including the PID number, trial center, baseline value, and all post-baseline (including non-PCS) values. A listing of all AEs for patients with post-baseline PCS laboratory values will also be provided.

Table 5.12-2. Criteria for Potentially Clinically Significant Laboratory Results

Parameter	SI Unit	Lower Limit	Higher Limit
CHEMISTRY			
Albumin	g/L	< 0.9 × LLN	> 1.1 × ULN
Alanine aminotransferase	U/L	—	≥ 3 × ULN
Alkaline phosphatase	U/L	—	≥ 3 × ULN
Aspartate aminotransferase	U/L	—	≥ 3 × ULN
Bicarbonate	mmol/L	< 0.9 × LLN	> 1.1 × ULN
Bilirubin, total	µmol/L	—	> 1.5 × ULN
Calcium	mmol/L	< 0.9 × LLN	> 1.1 × ULN
Chloride	mmol/L	< 0.9 × LLN	> 1.1 × ULN
Cholesterol, total	mmol/L	—	> 1.6 × ULN
Creatinine	µmol/L	—	> 1.3 × ULN
Glucose	mmol/L	< 0.8 × LLN	> 1.4 × ULN

Table 5.12-2. Criteria for Potentially Clinically Significant Laboratory Results

Parameter	SI Unit	Lower Limit	Higher Limit
Magnesium	mmol/L	$< 0.9 \times \text{LLN}$	$> 1.1 \times \text{ULN}$
Phosphate	mmol/L	$< 0.9 \times \text{LLN}$	$> 1.1 \times \text{ULN}$
Potassium	mmol/L	$< 0.9 \times \text{LLN}$	$> 1.1 \times \text{ULN}$
Protein, total	g/L	$< 0.9 \times \text{LLN}$	$> 1.1 \times \text{ULN}$
Sodium	mmol/L	$< 0.9 \times \text{LLN}$	$> 1.1 \times \text{ULN}$
Urea nitrogen	mmol/L	—	$> 1.2 \times \text{ULN}$
Uric acid	$\mu\text{mol/L}$	$< 0.9 \times \text{LLN}$	$> 1.1 \times \text{ULN}$
HEMATOLOGY			
Basophils, absolute cell count	$10^9/\text{L}$	—	$> 3 \times \text{ULN}$
Eosinophils, absolute cell count	$10^9/\text{L}$	—	$> 3 \times \text{ULN}$
Hematocrit	Ratio	$< 0.9 \times \text{LLN}$	$> 1.1 \times \text{ULN}$
Hemoglobin	g/L	$< 0.9 \times \text{LLN}$	$> 1.1 \times \text{ULN}$
Lymphocytes, absolute cell count	$10^9/\text{L}$	$< 0.8 \times \text{LLN}$	$> 1.5 \times \text{ULN}$
Mean corpuscular hemoglobin	pg	—	$> 3 \times \text{ULN}$
Mean corpuscular hemoglobin concentration	g/L	—	$> 3 \times \text{ULN}$
Mean corpuscular volume	fL	$< 0.9 \times \text{LLN}$	$> 1.1 \times \text{ULN}$
Monocytes, absolute cell count	$10^9/\text{L}$	—	$> 3 \times \text{ULN}$
Neutrophils, absolute cell count	$10^9/\text{L}$	$< 0.8 \times \text{LLN}$	$> 1.5 \times \text{ULN}$
Platelet count	$10^9/\text{L}$	$< 0.5 \times \text{LLN}$	$> 1.5 \times \text{ULN}$
Red blood cell count	$10^{12}/\text{L}$	$< 0.9 \times \text{LLN}$	$> 1.1 \times \text{ULN}$
White blood cell count	$10^9/\text{L}$	$< 0.7 \times \text{LLN}$	$> 1.5 \times \text{ULN}$

LLN = lower limit of normal value provided by the laboratory; SI = *Le Système International d'Unités* (International System of Units); ULN = upper limit of normal value provided by the laboratory.

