Colesevelam reduces serum LDL-C concentrations by binding bile acids in the intestine, impeding their reabsorption. As the bile acid pool becomes depleted, the hepatic enzyme, cholesterol 7- α -hydroxylase, is upregulated, which increases the conversion of cholesterol to bile acids. This causes an increased demand for cholesterol in the liver cells, resulting in the dual effect of increasing transcription and activity of the cholesterol biosynthetic enzyme, HMG-CoA reductase, and increasing the number of hepatic LDL receptors. These compensatory effects result in increased clearance of LDL-C from the blood, resulting in decreased serum LDL-C concentrations. Serum triglyceride concentrations may increase or remain unchanged. The mechanism by which colesevelam improves glycemic control is unknown. However, increasing evidence suggests that colesevelam, as a BAS, may function by signaling molecules in the liver and GI tract for lipid and glucose metabolism (13,14,15,16). The mechanism by which colesevelam is expected to reduce symptoms in GERD is by binding bile acids that are refluxed into the stomach and preventing the free bile acids from entering the esophagus and reacting with the esophageal mucosa.

There are no reported clinical efficacy studies with colesevelam in patients with GERD, or other upper GI disorders.

Colesevelam (as Welchol) has been evaluated for safety in clinical studies and via post-marketing pharmacovigilance. In general, colesevelam was safe and well-tolerated in adults with hyperlipidemia or type 2 diabetes mellitus, and in adolescents with familial hypercholesterolemia. Due to the large doses required for lipid lowering, and its local effects in the GI tract, most of the adverse events (AEs) related to colesevelam are GI in nature (constipation, flatulence, and dyspepsia). Most of these AEs were of mild or moderate intensity. In clinical lipid-lowering studies, the incidence of dyspepsia was greater at the higher doses (3.8 and 4.5 g/day).

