3.3.1.2 Exclusion Criteria

Patients who meet any of the following criteria will not be eligible to participate in the study:

1. Patient has a history of complete lack of GERD symptom response to PPIs in the past.
2. Patient reports epigastric pain or burning as his or her predominant symptom at the Screening Visit.
3. Patient has a history of gastroparesis, bowel obstruction, or is at risk for a bowel obstruction (e.g., patient has an organic GI motility disorder or a history of major GI surgery).
4. Patient has a history of serum triglycerides concentrations > 500 mg/dL on a fasting specimen, or has serum triglycerides concentrations > 500 mg/dL on a fasting specimen at Screening or any time during the Pretreatment Period.
5. Patient has a history of hypertriglyceridemia-induced pancreatitis.
6. In the Investigator's opinion, patient is susceptible to a deficiency of fat-soluble vitamins (especially vitamin D deficiency; e.g., the patient is African American or Hispanic or has osteoporosis, osteomalacia, etc.) and will be put at risk by receiving colesevelam for 8 weeks.
7. Patient has an active swallowing disorder that would prevent them from being able to swallow the study medication.
8. Patient has any alarm symptoms including but not limited to GI bleeding, anemia, vomiting, or unexpected weight loss any time during the Screening or Pretreatment Periods.
9. Patient has undergone surgery that meets any of the following criteria:

- a. Surgery of the GI tract (including gastric banding) other than an appendectomy, cholecystectomy, minor oral or rectal surgery (e.g., tonsillectomy, hemorrhoidectomy, rectocele repair) at any time before the Screening Visit
- b. An appendectomy during the 3 months before the Screening Visit or a cholecystectomy during the 6 months before the Screening Visit or minor oral or rectal surgery during the 30 days before the Screening Visit
- c. Non-GI surgery of the abdomen, pelvis, or retroperitoneal structures during the 6 months before the Screening Visit
- d. Thoracic surgery during the 6 months before the Screening Visit
- e. Other major non-GI surgery during the 30 days before the Screening Visit

10. Patient has previously undergone thoracic or abdominal radiotherapy.

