4.3.6 Clinical Laboratory Determinations

Blood and urine samples for clinical laboratory tests will be collected at the visits defined in the Schedule of Events ([Table 4.4-1](#)). The clinical laboratory evaluations will include the clinical chemistry, hematology, coagulation, and urinalysis parameters presented in [Table 4.3-1](#).

Table 4.3-1. Clinical Laboratory Tests

Clinical Chemistry	Hematology (CBC)	Complete Urinalysis
A1C	Hematocrit	pH and specific gravity
Albumin	Hemoglobin	Bilirubin
Alkaline phosphatase	Platelet count	Glucose
ALT	MPV	Ketones
AST	RBC count	Leukocytes
Bicarbonate	WBC count	Nitrites
BUN	WBC differential	Occult blood
Calcium	(% and absolute)	Protein
Chloride	Basophils	Urobilinogen
Total cholesterol	Eosinophils	
HDL cholesterol	Lymphocytes	
LDL cholesterol	Monocytes	
Creatinine	Neutrophils	
GGT	RBC indices	
Glucose	MCH	
Iron	MCHC	
LDH	MCV	
Magnesium	RDW	
Phosphorus	Coagulation	
Potassium	aPTT	
Sodium	PT	
Total bilirubin		
Total protein		
Triglycerides		
Uric acid		

Abbreviations: A1C = glycated hemoglobin; ALT = alanine aminotransferase; aPTT = activated partial thromboplastin time; AST = aspartate aminotransferase; BUN = blood urea nitrogen; CBC = complete blood count; GGT = gamma glutamyl transferase; HDL = high-density lipoprotein; LDH = lactate dehydrogenase; LDL = low-density lipoprotein; MCH = mean corpuscular hemoglobin; MCHC = mean corpuscular hemoglobin concentration; MCV = mean corpuscular volume; MPV = mean platelet volume; PT = prothrombin time; RBC = red blood cell; RDW = red cell distribution width; WBC = white blood cell

A blood sample for serum pregnancy testing will be collected from all female patients of childbearing potential at the Screening and EOT Visits, and a urine sample will be collected at the Randomization Visit (prior to dosing) and the Week 4 Visit. These pregnancy test results must be negative for patient eligibility. Ironwood may perform non-genetic analyses on existing plasma or serum samples for research purposes (e.g., bile in serum).

A urine screen for selected drugs of abuse (cocaine, barbiturates, amphetamines, opiates, benzodiazepines, and cannabinoids) and a serum alcohol screen will be performed at the Screening Visit.

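### SAP Table 5.12-2 has no potentially-clinically-significant criterion for triglycerides, and its MCH and MCHC limits cannot flag any patient

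*SAP*

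**What the plan says.** SAP 5.12.2 plans two kinds of laboratory output. Values and changes from baseline are summarized at each time point. In addition, "Clinical laboratory test values will be considered potentially clinically significant (PCS) if they meet either the lower-limit or higher-limit PCS criterion" in Table 5.12-2, and for those parameters "The incidence of change in clinical laboratory values from non-PCS at baseline to PCS post baseline will be tabulated". Two listings support this: patients with PCS values, and all adverse events in those patients.

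SAP 4.3.6 defines what is collected: "The clinical laboratory evaluations will include the clinical chemistry, hematology, coagulation, and urinalysis parameters presented in" Table 4.3-1. The chemistry column of that table includes "Triglycerides". The schedule of events places laboratory tests at Screening, Randomization, Week 4 and Week 8.

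Protocol 1.2 says of colesevelam: "Serum triglyceride concentrations may increase or remain unchanged". Protocol 3.3.1.2 excludes patients with "serum triglycerides concentrations > 500 mg/dL on a fasting specimen", whether in the history or found during Screening or Pretreatment. It also excludes a history of pancreatitis caused by high triglycerides.

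Table 5.12-2 has a chemistry block and a hematology block. Neither has a triglyceride row. In the hematology block, mean corpuscular hemoglobin and "Mean corpuscular hemoglobin concentration" each have a dash for the lower limit and > 3 x ULN for the upper. MCV, hemoglobin, hematocrit and red cell count use < 0.9 x LLN and > 1.1 x ULN.

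**The concern.** There are two separate problems in one table.

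First, a parameter without a row in Table 5.12-2 can never be PCS. Triglycerides therefore have no shift incidence, no PCS listing and no linked adverse event listing, although the protocol itself describes a possible rise under this drug and limits entry on it. Safety across three doses is a study objective. A count per arm of patients crossing a fixed limit is the natural way to compare doses on this kind of effect.

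Second, the MCH and MCHC rows state a rule that appears impossible to meet. A table reporting zero patients in every arm would look like reassurance but carry no information.

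**Working it through.** The documents give no figure to reproduce here. The check compares the two SAP tables row by row and then tests whether the MCH and MCHC limits can be reached.

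**1. Collected parameters against PCS rows**

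| Block | Collected (Table 4.3-1) | With a PCS row (Table 5.12-2) | Without a row |
|---|---|---|---|
| Chemistry | 25 | 18 | A1C, HDL, LDL, GGT, iron, LDH, triglycerides |
| Hematology | 15 | 13 | MPV, RDW |
| Coagulation | 2 | 0 | PT, aPTT |
| Total | 42 | 31 | 42 - 31 = 11 |

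Urinalysis is left out of this count.

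**2. Is the row lost in the file?** The chemistry rows are close to alphabetical, so triglycerides would fall between sodium and urea nitrogen. Those two rows are adjacent and intact, and the table closes with its footnote after the hematology block. SAP section 6, on changes from the protocol, does not mention the matter.

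**3. Why triglycerides differ from the other ten.** They are the only unlisted test for which the protocol both describes a possible rise under the drug and sets a numeric eligibility limit. Bilirubin is the other laboratory test with a numeric eligibility limit (> 1.5 x ULN, Protocol 3.3.1.2), and Table 5.12-2 uses the same > 1.5 x ULN for its PCS row.

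**4. What the remaining summaries can show.** SAP 5.1.1 provides mean, SD, median, minimum and maximum. As an illustration (assumed, not from the documents), take an arm of 65 in which k patients rise by 400 mg/dL and the others do not change. The mean change is 400k/65, and the SD is 400 x sqrt(k(65 - k)/(65 x 64)).

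- k = 1: mean 6.2, SD 400 x sqrt(64/4160) = 49.6, maximum 400
- k = 3: mean 18.5, SD 400 x sqrt(186/4160) = 84.6, maximum 400

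The maximum shows that a large rise occurred, but it is the same for one patient as for three. In real data the other patients also vary, so the number cannot be recovered from the mean and SD.

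SAP 7.1 adds a further difference. When end-of-study assessments are repeated or unscheduled visits occur, the summary uses the last non-missing value, whereas PCS determination uses all post-baseline values. A high triglyceride value followed by a lower repeat could drop out of the end-of-study summary, with no PCS analysis to retain it.

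**5. Can MCH or MCHC reach 3 x ULN?** The documents give no numeric ULN, so these are assumed ranges.

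- MCHC, ULN 350 to 370 g/L: 3 x 350 = 1050; 3 x 370 = 1110 g/L. This is more than 1 kg of hemoglobin per litre of red cells.
- MCH, ULN 32 to 35 pg: 3 x 32 = 96; 3 x 35 = 105 pg.
- Cross-check by MCH = MCV x MCHC, with MCHC at its own assumed ULN: the MCV needed runs from 96/370 x 1000 = 259 fL to 105/350 x 1000 = 300 fL.

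No value in these ranges is attainable. With no lower limit either, the two rows can flag no one.

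**6. Unit.** The SAP reports in SI units. Using 88.57 mg/dL per mmol/L, 500 mg/dL is 500/88.57 = 5.65 mmol/L.

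**The case against.** The strongest reply is that large triglyceride rises would still be seen. Summaries by visit include SD, minimum and maximum. SAP 7.1 puts every assessment in the data listings. Protocol 3.5.1.3 makes a laboratory change an adverse event if the investigator judges it clinically significant or it needs intervention, and SAP 5.12.1 tabulates those events by arm. This stands. It narrows the point to a missing threshold count and PCS listing, since none of these outputs counts patients over a common numeric limit.

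The table was also never exhaustive: 11 of 42 tests have no row. The protocol's wording on triglycerides is mild, the exclusions concern entry only, and the adverse event singled out in SAP 5.12.1 is constipation. That keeps the severity low. It does not explain why the one unlisted test with both a described rise and an entry limit was left out.

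The 500 mg/dL figure applies to fasting samples. Protocol 3.4.6 and 3.6.2 have patients take study drug after breakfast and before coming to the site, so Week 4 and Week 8 samples will usually follow a meal. This stands too, and any triglyceride row must allow for it.

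On MCH and MCHC, both are ratios of measures that already have two-sided limits, and no red-cell risk of the drug is documented. Little safety information is lost, but the rows still state a rule that cannot work.

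**Conclusion.** The point holds in a narrow form, as two independent table defects of low severity. Triglycerides lack a PCS criterion despite being collected, described as possibly rising and limited at entry. The MCH and MCHC rows guarantee zero incidence. The second conclusion rests on assumed reference ranges but holds throughout them. Efficacy, sample size, power and alpha are unaffected.

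A reader might infer more than the documents support:

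- **That no individual outlier would be seen, or that the dose comparison on triglycerides has nothing to go on.** The minimum and maximum, full listings and adverse event reporting contradict this.
- **That PT and aPTT are a neglected risk of the drug.** They are collected without a row, but the exclusion on fat-soluble vitamins stresses vitamin D. The documents nowhere mention vitamin K or link study drug to PT or aPTT. Warfarin appears only among the prohibited medicines.
- **That the MCH and MCHC limits contribute to the triglyceride gap.** They have no bearing on it.

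**What to change.** Amend Table 5.12-2 before unblinding, so that the limits are not chosen after the data are seen.

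- Add a triglyceride row. The reporting threshold is for the sponsor to choose; the only figure in the documents is the fasting entry limit of > 500 mg/dL (about 5.65 mmol/L). Present flags with fasting status where it was recorded.
- Replace the MCH and MCHC limits with attainable ones, for example the < 0.9 x LLN and > 1.1 x ULN already used for MCV.

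The cost is one added row, two edited rows and the matching output specifications, on data already collected. The downside is that some non-fasting triglyceride values will be flagged. Randomization should make these similar across arms, so they add noise to the comparison rather than favor one dose.

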5.12.3 Vital Sign Parameters

Vital sign values will be summarized for each assessment time point. Change from baseline values will be summarized for each assessment time point post baseline.

Vital sign values will be considered PCS if they meet both the observed-value criterion and the change-from-baseline criterion listed in [Table 5.12-3](#). The incidence of PCS vital signs will be tabulated for patients with a baseline value and at least 1 post-baseline assessment. A supportive listing of patients with PCS vital signs will be provided, including the PID number, trial center, baseline value, and all post-baseline (including non-PCS) values. In addition, a listing of all AEs that occurred in patients who had PCS vital sign values will be provided.

Table 5.12-3. Criteria for Potentially Clinically Significant Vital Signs

Parameter	Flag	Criteria^a	
		Observed Value	Change from Baseline
Sitting systolic blood pressure, mm Hg	High	≥ 180	Increase of ≥ 20
	Low	≤ 90	Decrease of ≥ 20
Sitting diastolic blood pressure, mm Hg	High	≥ 105	Increase of ≥ 15
	Low	≤ 50	Decrease of ≥ 15
Sitting pulse rate, bpm	High	≥ 120	Increase of ≥ 15
	Low	≤ 50	Decrease of ≥ 15
Weight, kg	High	—	Increase of ≥ 7%
	Low	—	Decrease of ≥ 7%

a. A post-baseline value is considered potentially clinically significant if it meets both the observed-value and the change-from-baseline criteria.

bpm = beats per minute.

5.12.4 ECG Parameters

ECG values will be summarized for baseline and the EOT Visit. Change from baseline values will be summarized for the EOT Visit. ECG values will be categorized as low, normal, or high based on reference ranges provided by the site. Shifts from baseline to end of study will be tabulated for the following categories: normal, abnormal not clinically significant, and abnormal clinically significant. ECG values will be PCS if they meet the higher limit PCS criteria listed in [Table 5.12-4](#). The incidence of change in ECG values from non-PCS at baseline to PCS post baseline will be tabulated for patients with non-PCS values at baseline and at least 1 assessment post baseline.

Table 5.12-4. Criteria for Potentially Clinically Significant ECG Parameters

ECG Parameter	Unit	Higher Limit
QRS duration	msec	≥ 150
PR interval	msec	≥ 250
QTc interval	msec	> 500

5.12.5 Other Safety Parameters

Any physical examination abnormality that the investigator considers to be potentially clinically significant will be reported as an AE. No separate analysis of Physical Examinations is planned.

5.13 DETERMINATION OF SAMPLE SIZE

The sample size per arm was determined by estimating the overall power of a linear trend test in a one-way design that included placebo and all the active treatment arms (500 mg BID, 1000 mg BID, and 1500 mg BID of IW-3718). The efficacy endpoint of interest in the previous Phase 2a study (ICP-3718-201) was change from baseline in daytime heartburn defined as the presence of heartburn since the patient awoke that morning (assessed in the evening) and assessed with an 11-point [0 to 10] NRS, where 0=none and 10=very severe. In that study, IW-3718 demonstrated treatment differences near 0.70 points for change over the treatment period (e.g., -0.73 vs. -1.38 for placebo and IW-3718, respectively), and standard deviations near 1.35 for the LSMS.

Employing these historical values, a study with 58 patients per arm (the expected number of patients at Week 8 given an enrollment of 260 patients) will have statistical power of at least 80% for the overall trend test (i.e., linear contrast) where the highest active treatment arm reflects 110% of the previously observed treatment difference and the lowest 2 active treatment arms reflect 55% of the same (two-sided, $\alpha=0.05$). At the proposed sample size, a subsequent pairwise comparison between placebo and an active treatment arm reflecting the previously observed treatment difference will have 80% statistical power (two-sided, $\alpha=0.05$).

6. CHANGES FROM ANALYSES PLANNED IN THE PROTOCOL

- a. One additional analysis population (the Randomized Population) was defined in the SAP that was not previously defined in the Protocol.
- b. Patient disposition will be summarized for the Randomized Population as opposed to the mITT Population as specified in the Protocol.

7. DATA HANDLING CONVENTIONS

7.1 REPEATED OR UNSCHEDULED ASSESSMENTS OF SAFETY PARAMETERS

If a patient has repeated assessments prior to the start of double-blind study drug, then the results from the final non-missing assessment made prior to the start of the double-blind study drug will be used as baseline. If end-of-study assessments are repeated or if unscheduled visits occur, the last non-missing post baseline assessment will be used as the end-of-study assessment for generating summary statistics. However, all post-baseline assessments will be used for PCS value determination as described above and all assessments will be presented in the data listings.

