3.3.2 Removal of Patients from Therapy or Assessment

A premature discontinuation will occur when a patient who has signed the ICF ceases participation in the study, regardless of circumstances, before completion of the Treatment Period.

A patient will be considered to have completed the study after receiving 8 weeks of treatment and completing the End-of-treatment (EOT) Visit at Day 57. A window of +3 days will be allowed for the EOT visit; if a patient completes the EOT Visit prior to Day 57, this will be considered a protocol deviation.

Patients will be informed that they are free to withdraw from the study at any time and for any reason. The Investigator may remove a patient from the study if, in the Investigator's opinion, it is not in the best interest of the patient to continue the study. Patients may also be discontinued from the study by the Investigator or the Sponsor at any time for any reason, including the following:

- Failure to meet an inclusion/exclusion criterion that is clinically relevant and affects patient safety
- Adverse event(s)

- Protocol violation, including lack of compliance
- Insufficient therapeutic response (lack of efficacy)
- Lost to follow-up (every effort must be made to contact the patient; a certified letter must be sent)
- Withdrawal of consent (attempts should be made to determine the reason for the patient withdrawing consent if possible)
- Study termination by the Sponsor
- Other reasons (e.g., administrative reasons or pregnancy)

The date the patient is withdrawn from the study and the reason for discontinuation will be recorded on the study termination form of the electronic case report form (eCRF). Patients who discontinue from the study for any reason should complete the assessments required at the EOT Visit at the time of their discontinuation. Patients who discontinue from the study will be followed until resolution of all of their AEs or until the unresolved AEs are judged by the Investigator to have stabilized. Study centers should make a reasonable effort to follow any pregnant patients until delivery or end of the pregnancy.

If a patient does not return for a scheduled visit, the study center should contact the patient. An effort must be made to contact the patient, including sending a certified letter. In every case, the patient outcome, including lost to follow-up information, will be documented.

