5.6 MEASUREMENT OF TREATMENT COMPLIANCE

The first dose of study medication will be taken in clinic at the Randomization Visit (Day 1). Patients should take their second dose that evening immediately upon completion of dinner. During the Treatment Period, patients will take study medication BID at home, in the morning (immediately upon completion of breakfast) and in the evening (immediately upon completion of dinner), even on study visit days. The last dose of study medication will be taken the morning of the EOT Visit. The double-dummy dosing requires all patients to take three tablets for each dose.

Dosing compliance for the Treatment Period is defined as the number of tablets taken by a patient during the Treatment Period divided by the number of tablets that were expected to be taken during the Treatment Period multiplied by 100. The total number of tablets taken will be calculated as total number of tablets dispensed minus total number of tablets returned minus total number of tablets lost. The total number of tablets expected to be taken during the Treatment Period is the number of days between the date of first dose taken and the date of last dose taken, inclusive, multiplied by 6 (multiplied by 6 minus 3 if the last dose is a morning dose). Patients will be included in the period summary only for the periods they were on study (i.e., the periods that are prior to or contain the last dose date).

Descriptive statistics for study drug compliance will be presented for the Safety Population by treatment group.

Patients will record their PPI administration each day (once daily) in their eDiary. PPI compliance for a specified period is defined as the number of days for which a patient answered Yes to the PPI administration question in the eDiary divided by the total number of days for which the patient provided an answer (Yes or No) to the PPI administration question in that period multiplied by 100. PPI compliance will be summarized by treatment group for the Safety Population.

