5.12 SAFETY ANALYSIS

Safety analyses will be performed using the Safety Population. Safety data summaries will be presented for each treatment group as well as for IW-3718 overall.

For analysis of safety parameters, the last non-missing value before the first dose of double-blind study drug will be used as baseline.

[Table 5.12-1](#) below presents the visits assigned for the safety analysis corresponding to the range of trial days (window) during which an actual visit may have occurred.

Table 5.12-1. Visit Time Windows for Safety Analysis

Derived Visit	Scheduled Test / Visit Day^a	Window
Baseline	Day 1	Days \leq 1
Day 15 Visit	Day 15	Days [2, 22]
Day 29 Visit	Day 29	Days [23, 43]
Day 57 Visit	Day 57	Days \geq 44
End of Treatment ^b	Final or termination visit	

a. Relative to the date of randomization; Day 1 = the day of randomization.

b. “End of Treatment” will be presented in analysis tables for safety parameters, including clinical laboratory and vital signs.

Test/Visit Day will be calculated as follows: test/visit date – date of randomization.

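### SAP 7.1 lets repeat tests taken after study drug has stopped serve as end-of-study safety values, so end-of-treatment means and the ECG shift table can describe off-drug results

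*SAP*

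**What the plan says.** SAP 7.1 covers repeated end-of-study assessments and unscheduled visits. In those cases, "the last non-missing post baseline assessment will be used as the end-of-study assessment for generating summary statistics". The next sentence makes an exception: "all post-baseline assessments will be used for PCS value determination as described above and all assessments will be presented in the data listings".

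SAP 5.12, Table 5.12-1, assigns safety results to visits. The Day 57 window runs from Day 44 with no upper limit. The End of Treatment row is defined only as "Final or termination visit", and its footnote says that it "will be presented in analysis tables for safety parameters, including clinical laboratory and vital signs". Neither entry refers to the date of last dose.

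SAP 5.6 fixes the time of that dose: "The last dose of study medication will be taken the morning of the EOT Visit".

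For ECG, SAP 5.12.4 states "ECG values will be summarized for baseline and the EOT Visit", and then "Shifts from baseline to end of study will be tabulated for the following categories": normal, abnormal but not clinically significant, and abnormal and clinically significant. This is the only shift table in the SAP.

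Protocol 3.5.1.3 makes laboratory, vital-sign, examination and ECG changes adverse events if the investigator judges them clinically significant or they need intervention. Under Protocol 3.3.2, patients who discontinue "will be followed until resolution of all of their AEs or until the unresolved AEs are judged by the Investigator to have stabilized". Protocol 3.5.1.3 has a similar follow-up rule for serious adverse events.

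**The concern.** Repeat tests are not a random sample of results. A patient with a normal EOT result has little reason to be tested again. A patient with an abnormal result may be called back, and follow-up then continues until the finding resolves or stabilises. A rule that always takes the last value will therefore tend to replace abnormal values with later ones. Because dosing ends on the day of the EOT Visit, those later values are also off treatment.

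A row labelled End of Treatment could then describe patients some time after treatment. The trial is meant to describe safety across three doses and placebo. If on-treatment abnormalities were more frequent at higher doses, selective replacement would narrow the differences between arms in the summaries that it touches.

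**Working it through.** The plan gives no figure to reproduce here, so the check is to trace the rule and then illustrate its size.

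**Step 1: can an off-drug value become the end-of-study value?** Yes.
- A completer takes the last dose on the morning of the EOT Visit. A laboratory repeat some days later is still a post-baseline assessment, and SAP 7.1 selects it.
- Suppose a patient stops on Day 20 and has a follow-up test on Day 50. SAP 7.1 makes that test the end-of-study value, and it also falls in the Day 57 window (Day 44 onward), 30 days after the last dose.
- SAP 7.1 speaks only of the end-of-study value. Table 5.12-1 gives no rule for several values in one window, so whether the Day 57 row also takes the last value is left open.

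**Step 2: which outputs change?**

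| Output | Affected? |
|---|---|
| End-of-treatment mean and change from baseline (laboratory, vital signs, ECG) | Yes |
| ECG shift, baseline to end of study (SAP 5.12.4) | Yes |
| PCS incidence (SAP 5.12.2 to 5.12.4) | No, uses all post-baseline values |
| Treatment-emergent adverse events (SAP 5.12.1) | No |
| Listings | No |
| Scheduled Week 2 and Week 4 results, in windows Days 2–22 and 23–43 | No |

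**Step 3: where do the unaffected outputs give no cover?**
- SAP Table 5.12-2 has no row for triglycerides, LDL, GGT, PT or aPTT, although SAP Table 4.3-1 collects all of them. Summary statistics are their only planned laboratory table. Protocol 1.2 says that triglycerides may rise on the active substance.
- The ECG PCS criteria cover only QRS, PR and QTc. EOT is the only scheduled post-baseline ECG. Any other ECG abnormality that is normal on repeat leaves the categorical ECG tables. It then appears only in listings, or in the adverse event tables if reported as an event.

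**Step 4: illustration.** n = 65 per arm (Protocol synopsis). Two inputs are assumptions: k, the patients abnormal at the scheduled EOT test, and f, the share of them repeated off drug and found normal.

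Share shown as abnormal: k/n if the scheduled value is kept, k(1 − f)/n under SAP 7.1.

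| k | Scheduled value kept | SAP 7.1, f = 0.5 | SAP 7.1, f = 1 |
|---|---|---|---|
| 2 | 2/65 = 3.1% | 1/65 = 1.5% | 0% |
| 4 | 4/65 = 6.2% | 2/65 = 3.1% | 0% |
| 6 | 6/65 = 9.2% | 3/65 = 4.6% | 0% |

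For a mean, assume that each such patient lies 2 × ULN above normal and returns to normal. The arm mean falls by 2kf/65 in ULN units:
- f = 0.5: 0.031 (k = 2), 0.062 (k = 4), 0.092 (k = 6)
- f = 1: 0.062, 0.123, 0.185

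For triglycerides, assume that 5% to 15% of an arm is repeated, with a mean fall of 100 mg/dL. The arm mean moves by 0.05 × 100 = 5 to 0.15 × 100 = 15 mg/dL.

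**The case against.** A reader might infer that the rule hides a dose-related safety signal. The documents do not support that. The mechanism works mainly through abnormalities followed because they are adverse events, and those events stay in the incidence tables by arm whatever a repeat shows. SAP 7.1 itself keeps every post-baseline value for PCS determination and listings. The laboratory and vital-sign PCS listings also show all post-baseline values, and the adverse events of those patients are listed as well. This part of the objection stands, and it limits the point to descriptive summaries and one ECG table.

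A reader might also infer that the bias always runs toward normal, or is largest in a particular arm. Neither is shown. A last value can be worse than the scheduled one, and no arm-level repeat rates are given.

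Opportunity is limited too. Protocol 3.6.3 schedules only a telephone call 7 days after EOT, with no off-drug laboratory or ECG visit. Follow-up to resolution is written for patients who discontinue and for serious events. A mid-treatment unscheduled value would normally be superseded by the later EOT value. All of this stands, and it means that the effect may be small.

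Finally, taking the last non-missing value is a pre-specified convention applied alike in every arm, and some repeats correct a poor sample. The laboratory footnote to the Schedule of Events allows a fasted lipid panel after a non-fasted triglyceride exceedance. That is a reason to allow replacement of invalid samples. It is not a reason to let every later value replace the visit value.

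**Conclusion.** The point holds in a limited form. As written, the SAP can place post-treatment values in rows labelled End of Treatment, and the values replaced are likely to be the abnormal ones. A lean toward normal in end-of-treatment means, changes from baseline and the ECG shift table is expected but not certain.

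The effect is dilution in descriptive output. Exposure is greatest for laboratory parameters without a PCS criterion and for the ECG normal/abnormal classification.

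Its size cannot be stated from the documents, because they give no rate of unscheduled repeats. The illustrations rest on assumed numbers of abnormal patients, shares normalising and falls on repeat. They show only how the summaries would move under those assumptions.

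**What to change.** Amend SAP 7.1 and Table 5.12-1 as follows:
- Define the End of Treatment and Day 57 value as the one from the scheduled Week 8/EOT or early-termination visit, and close the window at that visit.
- Let a repeat replace it only when the first sample is documented as invalid, for example a non-fasted lipid panel or a haemolysed specimen.
- If there is no such visit value, use the last value obtained on treatment, for example within 1 day of the last dose. That matches the treatment-emergent window in Protocol 3.7.5.1.
- Keep all later values for PCS evaluation and listings, as now.

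The cost is one revised rule and a small programming change, with no change to data collection. A few patients whose only late value is off drug would drop out of the end-of-treatment summary. An early-termination visit held some days after the last dose would still give an off-drug value, and a table footnote on days since last dose would make that visible.
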